8.3.2 Exclusion Criteria

Eligible subjects must **not** meet any of the following exclusion criteria:

1. Any other type of glaucoma other than primary open-angle glaucoma as defined in inclusion criteria 3
2. Severe POAG patients with a macular degeneration and visual field loss of -20dB or worse
3. Exsudative age-related macular degeneration, instable macular degeneration 30 days prior to inclusion or macular edema
4. Retinal detachment
5. Corneal diseases
6. Diabetes mellitus
7. Connective tissue diseases

8. History or evidence of severe inflammatory eye diseases (i.e. uveitis, retinitis, scleritis) in one or both eyes within 6 months prior to ARGOS-IO pressure sensor implantation.
9. Intraocular surgical procedure(s) within 6 months prior to ARGOS-IO pressure sensor implantation or any surgical procedure such as refractive eye surgery that can affect the assessment of IOP by Goldmann Applanation tonometry.
10. History of eye tumor.
11. Ocular disease other than glaucoma that may affect assessment of visual acuity and/or IOP by Goldmann Applanation tonometry (choroidal hemorrhage or detachment, lens subluxation, thyroid ophthalmopathy).
12. Anterior chamber configuration that puts the subject at high risk to develop an angle closure glaucoma.
13. History of extensive keloid formation.
14. Severe dry eye syndrome.
15. Subjects who will need to undergo ancillary procedures in the study eye at the time of implantation or during the post-operative study period.
16. Any known intolerance or hypersensitivity to topical anesthetics, mydriatics, plaster or silicone (component of the device).
17. Existence of other active medical eye implant and/or other active medical implants in the head/neck region.
18. Any contraindications for IOL implantation such as choroidal hemorrhage, concomitant severe eye diseases, excessive vitreous loss, extremely shallow anterior chamber, microphthalmos, non-age-related cataract, posterior capsular rupture, severe corneal dystrophy, untractable IOP, zonular separation, color vision deficiencies
19. Severe generalized disease resulting in a life expectancy shorter than a year.
20. Any clinical evidence that the investigator feels would place the subject at increased risk with the placement of the device.
21. Currently pregnant or breastfeeding.

	Clinical Investigation Plan ARGOS-02	Revision C <hr/> Page 65 of 106
---	---	------------------------------------

22. Participation in any study involving an investigational drug or device within the past 30 days or ongoing participation in a study with an investigational drug or device.
23. Patients who are not suitable for the study based on the surgeon's evaluation.
24. Patients unable or unwilling to understand or comply with required study procedures.
25. Patients with psychiatric disorders influencing their judgment or autonomy
26. Subject and/or an immediate family member is an employee of the investigational site directly affiliated with this study, the sponsor or the contract research organization.
27. Enrollment of the fellow eye in this clinical study.

8.3.3 Discontinuation or Withdrawal Criteria

8.3.3.1 Study stopping rules

As described in section 9, the study will be conducted in two stages. In the first stage, 11 subjects will receive ARGOS-IO implants, after which implantation will be halted. Once these subjects have completed their 3 months follow-up visits, the interim results will be evaluated by the DSMB. The study will be stopped for safety reasons if at the time of the interim analysis two or more of these 11 subjects have had SADEs or if the DSMB otherwise determines that severe safety risks to the subjects exist.

If more than two patients in the first stage of the study experience SADEs, the study will be stopped for safety reasons.

The study may be discontinued at any time for administrative reasons; if new negative data about the investigational device resulting from this or any other studies becomes available; and/or on advice of the DSMB, the sponsor, the investigators, and/or the EC or regulatory authorities.

If the study is prematurely terminated or suspended, the sponsor will promptly inform the investigators, the Regulatory Authorities and the ECs of the reason for termination or suspension. If the study is prematurely terminated for any reason, the investigator should promptly inform the study subjects and assure they receive appropriate therapy and/or follow-up.

The study can be terminated at any time for any reason by the sponsor.

 Implandata Ophthalmic Products GmbH	Clinical Investigation Plan ARGOS-02	Revision C
		Page 66 of 106

8.3.3.2 Screen Failures

Screen failures are subjects who have signed the informed consent form but fail to meet eligibility criteria for enrolment e.g. they do not meet one or more of the inclusion criteria or do meet one or more of the exclusion criteria. Such subjects will return to standard treatment and will not be enrolled in the study. The only data collected on them will be the date of their screening visit, the date they gave informed consent and reason they are a screen failure. This data will be entered on the demography and study discharge pages in the CRF.

8.3.3.3 Premature subject withdrawal

Subjects will be informed that they have the right to withdraw from the study at any time. The investigator must determine whether voluntary withdrawal is due to safety concerns.

All subjects who withdraw from the study after implantation and before completing the follow-up visits per protocol will be considered to be drop-outs. Subjects who drop-out or are withdrawn after implantation will not be replaced. Unless the patient revokes his/her permission to use it, any data collected up to the point of the patient's withdrawal will be included in the safety analysis. The data of all subjects who undergo implantation of the ARGOS-IO pressure sensor will be included in the efficacy analysis under the Full Analysis Set.

A patient will be withdrawn for any of the following reasons:

- The patient withdraws informed consent.
- It is determined during surgery that the patient is not feasible for ARGOS-IO pressure sensor implantation.
- The ARGOS-IO pressure sensor must be removed or replaced for any reason.

If the patient permits, all end-of-study assessments indicated in the visit schedule should be performed for implanted early discontinuing subjects.

Any subject who has been discontinued from the study because of an AE related to a study device or procedure will be followed as deemed appropriate by the investigator until resolution or stabilization of the event. This will be documented in the medical chart and in the CRF. Any patient who has been discontinued from the study because of an AE not related to a study device or procedure will be followed as deemed appropriate by the investigator.

 Implandata Ophthalmic Products GmbH	Clinical Investigation Plan ARGOS-02	Revision C
		Page 67 of 106

The investigator will classify the termination reason of each subject at the end of the study in the termination page of the CRF according to the following:

- AE
- Non-compliance with clinical investigation plan (CIP)
- Lost to follow up
- Voluntary withdrawal not for AE
- Other reason.

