2.6 Handling of Screening Failures and Drop-outs

Screen failures are patients who have signed the informed consent form but fail to meet eligibility criteria for enrolment, e.g., they do not meet one or more of the inclusion criteria or do meet one or more of the exclusion criteria. Such patients will be replaced.

Patients will be informed that they have the right to withdraw from the study at any time. The investigator must determine whether voluntary withdrawal is due to safety concerns. All patients who withdraw from the study after implantation and before completing the follow-up visits per protocol will be considered as drop-outs. Patients who drop out or are withdrawn after implantation will not be replaced.

Reasons for withdrawal are:

- The patient withdraws informed consent,
- it is determined during surgery that the patient is not feasible for ARGOS-IO pressure sensor implantation,
- the ARGOS-IO pressure sensor must be removed or replaced for any reason,
- patient becomes pregnant between screening and surgery.

Unless the patient revokes his/her permission to use it, any data collected up to the point of the patient's withdrawal will be included in the safety analysis. The data of all patients who undergo implantation of the ARGOS-IO pressure sensor will be included in the efficacy analysis under the Full Analysis Set.

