2.11 Handling of Changes to Study Protocol

All changes of study protocol will be documented by amendments. If an amendment implies changes in the SAP, the SAP will be adapted and the adaptation will be documented in the document history.

3. Technical Aspects and Coding Conventions

All programmes will be written using SAS version 9.3 or higher. For the final analysis, tables, figures and listings will be provided in separate documents with own table of contents. For the interim analyses the separation is not mandatory. A minimum font size of 8 points will be used for the tables and figures, corresponding to a linesize of 140 digits and a pagesize of 52 lines for an output in DIN A4 format. For listings, a standard font size of 8 points with the linesize and pagesize as defined above will be used to produce the output in DIN A4 format.

The default summary statistics for quantitative variables will be the number of observations (n), mean, standard deviation (SD), median, minimum (min) and maximum (max) for those patients with data available. Additionally, the 1st and the 3rd quartiles (Q1 and Q3, respectively) may be calculated in some cases.

All summary statistics will be presented to one decimal place more than the raw value, except for the minimum and maximum values that will be presented with the same decimal precision as the raw value. Percentage values are to be presented to one decimal place.

Percentages will be presented with two decimal places. For the calculation, The number of all patients in a specified population or treatment group is used as denominator. The denominator will be specified in a footnote to the tables for clarification if necessary.

For qualitative variables (i.e. categorical data), the number (n) and percentage (%) of patients with non-missing data per category will be the default summary presentation, and where appropriate and present, the number of missing values as a “Missing” category.

Content of free-text fields will only be provided in listings but not in tables.

If the eCRF is changed by deletion of existing items, by addition of new items or by change of the response options for an item, this information will be given in the footer of the table along with the number of subjects affected by the change of the eCRF.

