4.1 Analysis Populations

Within the framework of this study, the following two main populations are analysed:

- **Safety Population:** consists of all patients with attempted implantation of the ARGOS-IO implant, whether or not successful.
- **Full Analysis Set (FAS):** The FAS population comprises all subjects in whom an ARGOS-IO pressure sensor was successfully implanted. Measurements recorded by the patient will not

be included into the evaluation of the FAS population. Additional information about the drop-outs: all patients who revoke their consent and agreement preoperatively will be regarded as screen failures and will not be included in the statistical evaluation. All patients who revoke their consent and agreement postoperatively will be considered withdrawals and their data will be evaluated in the safety analysis.

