5.1 Handling of Missing Data

All data of the patients will be used as available. All analyses will be performed on observed cases only. Missing data will not be replaced. Implausible values will be only excluded from the analysis if reasonable. The reason for exclusion will be given in the footer of the table or description of the figure.

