7.4 Evaluation of Secondary Safety Variables

Safety will be described in detail by frequency, seriousness, severity, nature and duration of adverse events based on the safety evaluation set. Number of adverse events as well as the number and relative frequency of patients reporting adverse events will be tabulated by system organ class and preferred terms. The same table will be prepared for serious adverse events. In addition, the number and relative frequency of patients reporting adverse events will be tabulated by system organ class and preferred terms in dependence on the worst severity and worst causal relationship. Furthermore, number of adverse device effects as well as the number and frequency of patients reporting adverse device effects will be tabulated by system organ class and preferred

terms and not by event description as stated in the protocol. Separate tables will be provided for events occurring 3, 6 and 12 month following implantation.

SADEs. SAEs leading to discontinuation as well as the nature and duration of AEs will be provided in listings only. The duration of adverse events will be calculated as follows:

$$\text{Duration of AE} = \text{Stop date of AE} - \text{Start of AE} + 1.$$

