8.2 Changes in the Planned Analysis

Departing from the planned analysis, the first DSMB meeting was conducted after 6 patients had completed Visit 4. The sponsor of this trial was enlightened that it is necessary to increase the overall sample size if this first DSMB meeting corresponds to a prepond analysis of the first stage of Simon's two stage design in order to maintain the type I and type II error. The report provided for this DSMB meeting comprised the listings and tables in the DSMB charter plus a table summarizing the compliance of subjects.

The second DSMB meeting was conducted after 11 patients completed Visit 5 (one month after implantation of the medical device). The report provided for this DSMB meeting comprised the listings and tables in the DSMB charter minus the summary of anterior segment examination results, posterior examination results, GAT measurements and ARGOS-IO measurements.

The first interim analysis independent from the DSMB was conducted after 21 subjects completed Visit 5 (one month after implantation of the medical device). The report provided comprised the listings and tables in the DSMB charter plus:

- Summaries of visual field and visual acuity results at screening and follow-up visits
- More detailed information about medical history, concomitant illnesses and previous/concomitant medications
- More detailed information about adverse events
- Additional summaries of GAT measurements and ARGOS-IO measurements including limits of agreement per visit and for all visits

The limits of agreement were provided in a separate document with corresponding table and figures. If multiple ARGOS-IO system measurements have been made at time points for which paired GAT/ARGOS-IO system measurements were to be compared, the mean of the replicate ARGOS-IO system measurements were used for agreement evaluation. Subsequently, this analysis was repeated by using the first replicate ARGOS-IO system measurement instead of the mean of the replicate measurements.

The second interim analysis independent from the DSMB was conducted after all subjects completed Visit 9 (6 months after implantation of the medical device). The report provided comprised the same tables and listings as the report for the interim analysis conducted after 21 subject completed Visit 5.

A. APPENDICES

List of Tables

Table 1	Disposition of patients (SES, FAS)
Table 2	Patient recruitment by month and by site
Table 3	Premature terminations

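### Withdrawing every patient whose sensor is removed or replaced ends scheduled collection of new adverse events but keeps the patient in the denominator, so 12-month AE/ADE incidences can be slightly too low (minor)

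*Protocol*

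**What the plan says.** **Withdrawal rule.** Protocol 8.3.3.3 withdraws a patient if "The ARGOS-IO pressure sensor must be removed or replaced for any reason". SAP 2.6 carries the same trigger: "the ARGOS-IO pressure sensor must be removed or replaced for any reason". Withdrawn patients are not replaced, and both sections admit their data to the safety analysis up to the point of withdrawal. Protocol 8.6 provides for explantation whenever it is medically indicated.

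**What remains after withdrawal.**
- One assessment, if the patient agrees (Protocol 8.3.3.3): "If the patient permits, all end-of-study assessments indicated in the visit schedule should be performed for implanted early discontinuing subjects". No date is set for it.
- Follow-up of events already known: the event behind the discontinuation (8.3.3.3), recorded AEs for 2 years after surgery (11.1.3) and ongoing AEs (12.13).
- SAE reporting from implantation onwards with no end date, but also with no visits attached (11.1.4).
- AE documentation until discharge from the study (11.1.3). The text does not say whether a withdrawn patient counts as discharged.

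**Visits.** Protocol 8.1.1 and SAP 2.3 say that all patients who receive an implant return for 10 follow-up visits. Neither section mentions the exception that the withdrawal rule creates.

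**Analysis.** The safety population "consists of all patients with attempted implantation of the ARGOS-IO implant, whether or not successful" (SAP 4.1). For percentages, SAP section 3 states: "The number of all patients in a specified population or treatment group is used as denominator". SAP 5.1 adds: "All analyses will be performed on observed cases only. Missing data will not be replaced". SAP 7.4 sets the output: "Separate tables will be provided for events occurring 3, 6 and 12 month following implantation". SAP 5.2 deals with drop-outs only through the critical value for the primary endpoint.

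**The concern.** Withdrawal here depends on the device outcome. Observation is cut short in the patients whose implant had to come out or be exchanged, who are among the most informative about safety between 3 and 12 months, a stated secondary objective. Because they stay in the denominator, a later event that nobody records counts as no event. The error can only lower the incidence, and the AE tables as planned do not show it.

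There is also a patient-care side. Protocol 6.4 treats removal as carrying the same risks as implantation, and a replacement sensor is a new exposure. The rule takes the patient off scheduled study visits at that moment.

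The rule also sits oddly with the rest of the plan. The AE form in Protocol 11.1.3 treats device removal and study withdrawal as two separate actions. Under Protocol 9.7, patients already implanted continue to be followed even if the whole study is stopped.

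**Working it through.** **Inputs**
- N = 22 implanted patients (Protocol 9.2; SAP 2.9 and 5.2).
- Follow-up visits on days 1, 3, 10, 30, 60, 90, 120, 180, 240 and 360 (Protocol 8.1.1).
- Status reported in SAP 8.2: "The second interim analysis independent from the DSMB was conducted after all subjects completed Visit 9 (6 months after implantation of the medical device").
- Assumed, because the documents give no figure: the number of patients explanted or replaced, the true incidence of each event type, and the shape of the hazard.

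**The plan's own N.** For the two-stage rule (continue with at least 10 of 11 SADE-free, succeed with at least 20 of 22), the exact binomial gives a type I error of 0.0497 at p0 = 0.75, power of 0.8001 at p1 = 0.94 and an expected sample size of 13.17 under p0. The Protocol states 5%, 80% and 13.2, so N = 22 reproduces as planned.

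**Ceiling.** One patient whose first event of a given type falls after withdrawal and goes unrecorded lowers the incidence by

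1/N = 1/22 = 0.0455, that is 4.5 points.

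If failed implantation attempts raise the safety population to 23 or 24, this becomes 4.3 or 4.2 points.

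**Window at risk.** If everyone completed Visit 9 (day 180), the visits that can be lost are V10 and V11: 2 of 10 follow-up visits and 360 − 180 = 180 of 360 days.

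**Illustration.** Take one patient with the sensor removed at day 180, a constant hazard, true 12-month incidence p, and every later event missed. The chance that the first event falls between day 180 and day 360 is

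(1 − p)^0.5 − (1 − p),

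and dividing by 22 gives the expected understatement.

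| p | (1 − p)^0.5 − (1 − p) | Divided by 22 |
|---|---|---|
| 10% | 0.9487 − 0.90 = 0.0487 | 0.22 points |
| 30% | 0.8367 − 0.70 = 0.1367 | 0.62 points |
| 50% | 0.7071 − 0.50 = 0.2071 | 0.94 points |

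The expression is largest at p = 75%: 0.50 − 0.25 = 0.25, or 0.25/22 = 1.1 points. A raised hazard after the removal surgery would move the figure towards the ceiling.

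**Scale.** The 95% half-width of a proportion with N = 22, by 1.96 × √(p(1 − p)/22), is about 13, 19 and 21 points at p = 10%, 30% and 50%. The illustrated understatement is less than a twentieth of that.

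**The case against.** The strongest reply is that little is at stake.

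- **No decision moves.** The 12-month tables are secondary and descriptive, and SAP 5.3 confines testing to the primary safety variable. The event that led to removal is already counted. This stands.
- **It may affect nobody.** No explantation rate is given. Protocol 6.4 says the implant was designed to be able to stay in the eye even if it fails, so a dead sensor alone need not trigger the rule. This stands.
- **Much is already covered.** The V11 column of the assessment schedule includes AE recording, so the optional assessment would pick up new events up to the day it is done. Known events are followed and SAEs remain reportable. This narrows the gap mainly to new, non-serious events after withdrawal but does not close it, because no further visits are scheduled.
- **The 10-visit statement could be read as keeping these patients in.** Protocol 8.1.1 and SAP 2.3 are general statements. The withdrawal trigger is specific and is repeated in the SAP, so the two conflict and the trigger is the likelier to be applied.
- **Reporting partly handles it.** Disposition, premature terminations and AEs leading to discontinuation are planned outputs, and SAP section 3 allows a denominator footnote where needed. A reader could piece the gap together, but the AE tables would not show it.
- **Version.** The SAP elaborates Protocol Rev. G, whereas the text available is Rev. C plus an addendum. SAP 2.6 confirms that the trigger survived. The AE-documentation wording is known only from Rev. C.

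Two stronger readings are tempting. A reader might infer that the primary SADE conclusion is biased. SAP 8.2, taken literally, rules that out in any material way, since Visit 9 lies beyond the 3-month window. A reader might also take 4.5 points as the expected bias. It is reached only if a first event of that type was certain to follow withdrawal and went unrecorded, and nothing in the documents suggests that.

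**Conclusion.** The point holds as a minor one. As written, the rule ends scheduled collection of new AEs because of a device outcome and leaves the patient in the denominator with no allowance for shorter observation. It also contradicts the plan's own statement that all implanted patients return for 10 visits.

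The effect on the 12-month AE and ADE incidences is likely under 1 point per such patient per event type (0.2 to 0.9 points in the illustration), with an absolute ceiling of 4.5 points. This rests on a constant hazard, removal at day 180, 12-month incidences of 10% to 50% and every later event missed.

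The primary 3-month decision and the 6-month tables are not materially affected if all subjects did complete Visit 9. If that sentence in SAP 8.2 meant only those still in the study, the earlier windows would be open too. The number of patients concerned is unknown and may be zero. The absence of scheduled AE collection is established for Rev. C wording only.

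**What to change.** **Preferred.** In Protocol 8.3.3.3 and SAP 2.6, delete removal or replacement of the sensor as a reason for study withdrawal. State that it ends measurements from the removed sensor only, and that scheduled safety visits and AE recording continue to V11 unless consent is withdrawn. This also removes the conflict with Protocol 8.1.1 and SAP 2.3.

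**Cost.** A Protocol amendment with ethics approval (12.3), possibly renewed consent (12.1), and a change of SAP wording. The visits are already scheduled for every implanted patient, though some explanted patients may decline them. With all subjects past Visit 9, an amendment can recover only V10 and V11 data not yet collected.

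**If an amendment is too late.** The SAP is finalised before hard lock of the database. It can still require a footnote to the 12-month AE tables (39, 42, 45 and 48) and to the ADE table (49, for which the list of tables states no time window), giving the number explanted or replaced and the number observed to day 360. The footnote shows the gap without filling it. It draws on disposition and termination data already planned, and if nobody was explanted or replaced it simply says so.
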